This visit is scheduled to take place Remotely on Day 7. Every effort should be made to complete the Day 7 visit requirements on Day 7; however, the visit may take place — if necessary +/- 1 days. Remote visits may include visits by the study staff to the participant or via phone/video conference. If remote visit not feasible or is not permissible under local rules or standards, the visit may be conducted in person.

- ~~SARS-CoV-2 Vaccination Status~~
- Concomitant medication review
- Collect and update contacts
- Daily Symptom Follow Up Questionnaire (daily until Day 28 then at **Weeks 8** and 12)
- Upper respiratory specimen collection (self-collection)
- Clinical Outcome Assessment
- Adverse event recording and reporting

C 9.4.5 Day 10 Visit- Remote

This visit is scheduled to take place Remotely on Day 10. Every effort should be made to complete the Day 10 visit requirements on Day 10; however, the visit may take place — if necessary +/- 1 days. Remote visits may include visits by the study staff to the participant or via phone/video conference. If remote visit not feasible or is not permissible under local rules or standards, the visit may be conducted in person.

- Daily Symptom Follow Up Questionnaire (daily until Day 28 then at **Weeks 8** and 12)
- Concomitant medication review
- Upper respiratory specimen collection (self-collection)
- Adverse event recording and reporting

C 9.4.6 Day 14 Visit – In Person

This visit is scheduled to take place In Person on Day 14. Every effort should be made to complete the Day 14 visit requirements on Day 14; however, the visit may take place — if necessary +/- 2 days

- ~~SARS-CoV-2 Vaccination Status~~
- Concomitant medication Review
- Daily Symptom Follow Up Questionnaire (daily until Day 28 then at **Weeks 8** and 12)
- Upper respiratory specimen collection
- Clinical outcome assessment
- Vital signs
- Physical exam
- Venous blood sampling (should be collected from all participants 22-26 hours after previous dose of upamostat or control)
 - Hematology
 - Chemistry
 - **Coagulation studies**
 - **Whole blood, plasma, and serum storage for possible future research**
 - **Pharmacokinetics**
- **ECG**
- Adverse Event Recording and Reporting

C 9.4.7 Day 28 Visit – In Person

This visit is scheduled to take place In Person on Day 28. Every effort should be made to complete the Day 28 visit requirements on Day 28; however, the visit may take place — if necessary +/- 4 days.

- ~~SARS-CoV-2 Vaccination Status~~
- Concomitant medication Review
- Daily Symptom Follow Up Questionnaire (daily until Day 28 then at **Weeks 8** and 12)
- Upper respiratory specimen collection
- Clinical outcome assessment
- Vital signs
- Physical exam
- **Pregnancy test**
- Venous blood sampling
 - Hematology
 - Chemistry
 - **Coagulation studies**
 - **Whole blood, plasma, and serum storage for possible future research**
- Adverse Event Recording and Reporting

C 9.4.8 Week 8 Visit – In Person

This visit is scheduled to take place In Person at Week 8. Every effort should be made to complete the Week 8 visit requirements at Week 8; however, the visit may take place — if necessary +/- 1 week.

- Concomitant medication review
- Daily Symptom Follow Up Questionnaire (daily until Day 28 then at **Weeks 8** and 12)
- Upper respiratory specimen collection
- Clinical outcome assessment
- Vital signs
- Physical exam
- Venous blood sampling
 - Hematology
 - Chemistry
 - **Coagulation Studies**
 - **Anti-SARS-CoV-2 IgM and IgG**
 - **Whole blood, plasma, and serum storage for possible future research**
- Adverse event recording and reporting

C 9.4.9 Week 12 ~~In Person OR Remote~~

This visit is scheduled to take place Remotely at Week 12. Every effort should be made to complete the Week 12 visit requirements at Week 12; however, the visit may take place — if necessary +/- 2 weeks.

- ~~SARS-CoV-2 vaccination status~~
- Concomitant medication review
- Daily Symptom Follow Up Questionnaire (daily until Day 28 then at **Weeks 8** and 12)
- Upper respiratory specimen collection (self-collection)
- Clinical outcome assessment
- Adverse Event Recording and Reporting

C 9.4.10 Unscheduled Visits – In Person or Remote

An unscheduled visit is defined as any visit to the clinical trial site outside of the protocol evaluation time points, where the participant is seen by a member of the clinical research staff. Participants will be encouraged to report any medical problems or discomfort to the study staff and may be instructed to return to the clinical trial site if they experience new or worsening COVID-19 symptoms or become infected with SARS-CoV-2 any time after enrollment. Remote visits may include visits by the study staff to the participant or via phone/video conference. If remote visit not feasible or is not permissible under local rules or standards, the visit may be conducted in person.

In the event of an unscheduled visit these procedures may be done according to clinical judgement:

If conducted remotely the following procedures may be performed:

- SARS-CoV-2 vaccination status
- Concomitant medication review
- Daily Symptom Follow Up Questionnaire
- Upper respiratory specimen collection (self-collection)
- Clinical outcome assessment
- Adverse event recording and reporting

If conducted in person following procedures may be performed:

- SARS-CoV-2 vaccination status
- Concomitant medication review
- Daily Symptom Follow Up Questionnaire
- Upper respiratory specimen collection
- Clinical outcome assessment
- Vital signs
- Physical exam

- Venous blood sampling
 - Hematology
 - Chemistry
 - **Coagulation studies**
 - **Whole blood, plasma, and serum storage for possible future research**
- **ECG**

Depending on the reason for the visit, the participant may have additional assessments or laboratory tests, as clinically indicated, or may be referred to the appropriate service for follow up.

C 10 ADVERSE EVENTS AND SERIOUS ADVERSE EVENTS

C 10.1.9 Pregnancy and Breastfeeding

Since there are no data regarding the use of upamostat in participants who are pregnant or breastfeeding, participants who are pregnant or breastfeeding are not eligible for the study. Participants of childbearing potential and participants who may impregnate their partners are required to follow the instructions for prevention of pregnancy provided in [Section C 6.3 Lifestyle Considerations](#).

If a participant becomes pregnant during the study (post-entry), administration of upamostat will be discontinued (if still taking) and study follow up will continue for the duration of the study. At the end of the pregnancy, outcome and adverse events for participant and infant will be recorded on the outcome eCRF.

C 12 PAUSE AND STOPPING CRITERIA

C 12.1 Individual Participant Pause and Stopping Criteria

The administration of IP to any participant may be stopped or paused for any SAE, clinically significant AE, severe lab abnormality or any medical condition that may indicate to the Investigators that IP continuation is not in the best interest of the participant. In addition, a subject in the clinical trial may discontinue study drug at their request for any reason. Every effort should be made to encourage subjects to remain in the study for the duration of their planned outcome assessments. Unless the subject withdraws the consent, those who discontinue study drug early will remain in the study. The reason for subject discontinuation will be documented in the case report form.

For an individual participant, the 14-day course of IP can be interrupted or stopped if there is a suspected drug-related event suggestive of QTc interval prolongation, anticoagulant effect, elevated liver enzymes or other, as per investigator or medical monitor discretion if it is deemed to be in the participant's best interest. All participants will receive baseline chemistry, liver enzyme, and coagulation studies as well as a baseline ECG.

The individual pause and stopping criteria will include (but not be limited to) the following:

- The subject worsens and requires treatment for worsening COVID-19 as recommended by the NIH COVID-19 Treatment Guidelines. Upamostat administration will be discontinued. All other study activities will continue, participant will not be withdrawn from the study.
- The subject worsens and requires hospitalization for worsening COVID-19. Upamostat administration will be discontinued. All other study activities will continue, participant will not be withdrawn from the study.
- QTc Interval: QTc increase >60 msec over baseline: repeat ECG within 48 hours and if >60 msec increase over baseline persists, IP will be discontinued. Participant will continue to be participate in follow up visits and, if necessary, until resolution or stabilization of the event.
- INR, PTT: increase over baseline > 2 Grades (per NIH DAIDS Table for Grading the Severity of Adult and Pediatric Adverse Events (DAIDS AE Grading Table) corrected Version 2.1, July 2017): pause therapy. Repeat INR and PTT within 48 hours of initial awareness of the abnormal laboratory value. If repeat testing \leq 2 Grades above baseline, may resume therapy until total of 14 days from start; missed days will not be made up. If repeat testing > 2 Grades above baseline, IP will be discontinued. Participant will continue to be participate in follow up visits and, if necessary, until resolution or stabilization of the event.
 - If increase over baseline 1 Grade: no additional follow up
 - If increase over baseline 2 Grades: In addition to scheduled PTT/INR testing on Day 3 and Day 14, participant will have coagulation testing on Day 28. If either PTT or INR is increased by \geq 1 Grade at Day 28, repeat testing will be performed at Week 8. Additionally, participant will be questioned at Day 7, Day 10, Day 14 visits, and

twice weekly from Day 14 until resolution of the coagulation abnormality to ≤ 1 Grade above baseline or Week 8 (whichever comes first), regarding bleeding, bruising or petechiae.

- Transaminases, bilirubin: increase over baseline >1 Grade above baseline: pause therapy. Repeat transaminase and bilirubin levels within 48 hours of initial awareness of the abnormal laboratory value. If repeat testing ≤ 1 Grade above baseline, may resume therapy until total of 14 days from start; missed days will not be made up. If repeat testing >1 Grade above baseline, IP will be discontinued. Participant will continue to be participate in follow up visits and, if necessary, until resolution or stabilization of the event.

C 12.2 Study and/or PSA Pause and Stopping Criteria

In addition to those listed in the Master Protocol, the study pause criteria listed in Table 1 will apply.

Table 1 Product Specific Criteria for Study Pause

Parameter	Investigational Products Related Adverse Events (AEs)	Action
Prolonged QTc Interval	QTc ^a >500 msec OR QTc ^a >60 msec above baseline on repeat ECG within 48 hours	Prompt reporting (within 24 hours of observation or report) Consider pause of the PSA PSRT to monitor for trend
ALT (SGPT), ALP (SGOT), or Total Bilirubin, High	> 1 Grade ^c increase in verified ^d abnormal AST, ALT, and total bilirubin in >2 patients	Prompt reporting (within 24 hours of observation or report) Consider pause of the PSA PSRT to Monitor for trend
PT, PTT, or INR, High (Not on anticoagulation therapy)	> 2 Grade increase in verified PT, PTT or INR >2 patients	Prompt reporting (within 24 hours of observation or report) Consider pause of the PSA PSRT to Monitor for trend

a Corrected QT may be calculated using any standardized formula or automated interpretation. The same methodology for calculating the QT interval should be applied throughout the participants enrollment in the study

c Per NIH DAIDS Table for Grading the Severity of Adult and Pediatric Adverse Events (DAIDS AE Grading Table) corrected Version 2.1, July 2017

d Verified definition: If no evidence of disease is present other than the abnormal laboratory value, the test must be repeated at least one time in order to be considered “verified”. The verification period will be a maximum of 48 hours after initial awareness of the abnormal laboratory value. When signs and symptoms are present, repeat test WILL NOT be needed

C 13 STATISTICAL CONSIDERATIONS

C13.1 Statistical Hypotheses

The primary hypothesis is that early treatment with upamostat among outpatients infected with SARS-CoV-2 can shorten time to sustained alleviation or resolution of Targeted COVID-19 symptoms (time to resolution) as compared to standard treatment.

The general statistical approach will compare outcomes among participants randomized to receive the active agent, upamostat, to outcomes among participants who were eligible to have been randomized to upamostat but who were randomized instead to any of the placebo arms enrolling at that time. This ensures that the comparison is limited to concurrently randomized participants eligible to receive upamostat.

C 13.4 Primary Endpoint/Estimand Analysis

The primary objective is to estimate the relative time to sustained alleviation or resolution of symptomatic COVID-19 infection for a participant that receives upamostat compared to a participant that does not receive upamostat.

The estimand of interest is the hazard ratio of a participant that has symptomatic COVID-19 with standard of care background therapy when starting treatment with upamostat compared to no upamostat. A hazard ratio greater than 1 indicates a shorter time to resolution of symptomatic COVID-19 infection.

The primary analysis population for upamostat is the modified intent-to-treat population, with a treatment arm consisting of all participants that were randomized to upamostat active treatment arm and received at least one dose of the active treatment. The control arm consists of all participants eligible to be randomized to upamostat that were randomized to placebo and received at least one dose of the placebo.

The primary analysis model is a Cox proportional hazards model for the time to alleviation or resolution of COVID-19 symptoms, with treatment arm (active upamostat vs placebo) as a covariate. The model estimated hazard ratio will be used as the estimator for the estimand of interest. The estimate and 95% confidence interval for the hazard ratio will be presented.

The primary hypothesis test is that upamostat increases the hazard (decreases time to resolution) of COVID-19 symptoms. A hypothesis test will be conducted for testing whether the upamostat hazard ratio is greater than 1 at a one-sided 2.5% level. One interim analysis will be conducted and a final analysis with type I error control over the two possible interims of 2.5%.

C 13.5 Outcome Measures and Statistical Analyses

C 13.5.1 Early Treatment

C 13.5.1.1 Primary Outcome

- Time to sustained alleviation or resolution of COVID-19 symptoms evaluated from Day 0 through Day 28 assessed via completion of a Daily Follow Up Symptom Questionnaire.

Sustained alleviation or resolution will be defined as the number of days from randomization to the first day the participant reports all symptoms as mild or none (≤ 1 or returning to pre-COVID-19 illness levels) for at least 3 consecutive days (the first day being considered the Event Day). Targeted symptoms will be used for analysis (Supplement 3 of the MP). Any patient that does not have alleviation or resolution of symptoms by Day 28 will be considered censored for alleviation or resolution at Day 28.

The primary efficacy analyses will be conducted using the modified intention to treat (mITT) population. The primary analysis is a Cox proportional hazards model with treatment assignment as a fixed covariate with a proportional effect. A one-sided p-value for the test of a hazards ratio of 1 compared to the alternative of a hazard ratio greater than 1 (upamostat reduces time to resolution of symptoms) will be presented and used for testing superiority. An interim analysis will be conducted when 50% of maximum enrollment has reached 28 days of exposure. A Kim-Demets (with parameter 2) spending function will be utilized for testing for superiority of upamostat at the interim and final analysis. At the interim analysis, futility analyses will be conducted, where enrollment to the upamostat cohort will be stopped if the predictive probability of superiority by the final sample size is less than 5%.

The hazard ratio for the time to resolution of COVID-19 will be presented with 95% confidence intervals. Additional sensitivity analyses for the primary analysis will utilize additional covariate adjustments in the Cox proportional hazards model.

C 13.5.1.2 Secondary Outcome: Clinical

For each analysis, a 5% two-sided significance will be used. 95% confidence intervals will be presented to summarize each effect estimate. Dichotomous outcomes will be summarized with relative proportions. Ordinal outcomes will be summarized with stacked bar plots, cumulative proportion graphs, and percentiles. Kaplan-Meier plots will be used for summarizing time to event outcomes. Continuous measures will be summarized box plots (means, medians, and inter-quartile ranges).

Each of the secondary analyses will be conducted using the modified intention to treat (mITT) population. Each analysis will be repeated using the per protocol population.

- Change in overall COVID-19 symptom severity score from Day 0 through Day 28

The overall symptom severity question on the Daily Symptom Follow Up Questionnaire will be used for this secondary endpoint. A mixed model repeated measure (MMRM) model will be

used to model the symptom severity score at each day using the baseline symptom score, participant, day, and treatment by day as covariates. The treatment effect by day will be summarized.

- Proportion of participants in each treatment group developing new COVID-19 symptoms rated as severe from Day 0 to Day 28

A Cox proportional hazards model will be used to analyze development of new severe symptoms. A new severe symptom is defined as scoring a 0 to 1 on any symptom in the questionnaire and subsequently scoring a 3 for that symptom (or a 2 for change in taste or smell). Treatment arm will be modeled with a proportional hazard effect. The hazard ratio will be summarized.

- Proportion of participants who report a return to usual state of health at Days 7, 14, 28, Week 8, and Week 12.

A Cox proportional hazards model will be used to analyze the time to return to usual state of health. Participants without symptomatic COVID-19 will be considered a 0 for return to usual state of health. Treatment arm will be modeled with a proportional hazard effect. The hazard ratio will be summarized.

- Proportion of participants who report a return to usual activities at Days 7, 14, 28, Week 8, and Week 12.

A Cox proportional hazards model will be used to analyze the time to return to usual activities. Participants without symptomatic COVID-19 will be considered a 0 for return to usual activities. Treatment arm will be modeled with a proportional hazard effect. The hazard ratio will be summarized.

- Proportion of participants in each treatment group hospitalized for COVID-19, as adjudicated prior to study unblinding.
- Number and proportion of participants hospitalized (all cause) from Day 0 to Day 28
- Number and proportion of participant deaths (all cause) from Day 0 to Day 28

Outcomes will be summarized with relative proportions

C 13.5.1.2 Secondary Outcome: Virological

- Comparison of active and placebo treatment groups in time to negative RT-PCR from Day 0 to Week 12

Time to negative RT-PCR will be defined as the time of the first of two consecutive readings below the lower limit of detection. A Cox proportional hazards model will be used to analyze the time to negative PCR.

C 13.5.1.3 Safety and Tolerability

An external DSMB will conduct interim reviews for safety. Monitoring of unblinded safety data (including AEs, SAEs, and selected laboratory measurements) will occur monthly throughout the study and will be conducted by the DSMB. Only the DSMB is authorized to evaluate unblinded interim efficacy and safety analyses.

Safety analyses will include:

- Incidence of Serious Adverse Events (SAE)
- Comparison between active and placebo treatment groups in proportion of all and \geq grade 3 adverse events as assessed by the National Institutes of Health, Division of AIDS Table for Grading the Severity of Adult and Pediatric Adverse Events (DAIDS AE Grading Table), corrected Version 2.1, July 2017.
- Incidence of AEs causing IP discontinuation
- Incidence of all-cause IP discontinuation or interruption
- Number of participants hospitalized due to adverse events regardless of cause

All adverse events will be listed by participant and will include:

- Event description
- Treatment group (active agent vs placebo)
- Clinician's assessment of severity and relationship to upamostat
- Outcome

The number and percentage of participants with AEs will be summarized for each treatment group. Overall treatment group differences may be compared using Chi-square tests or Fisher's exact tests.

Serious AEs, TEAEs, and hypersensitivity reactions will also be summarized. The counts and proportion of participants experiencing these events will be reported for each treatment arm. Treatment groups may be compared by Chi-square tests or Fisher's exact tests.

Permanent discontinuations or interruptions of upamostat due to AEs will be listed. The count and proportion of discontinuations of the study drug due to AEs will be reported.

Categorical safety measures including hospitalization will be summarized with counts and proportions of participants and may be compared by treatment using either a Chi-square test or a Fisher's exact test.

C 13.5.1.4 Exploratory

Prevalence and titer of anti-SARS-CoV-2 IgM and IgG antibodies at baseline and at Week 8 will be determined, and the effect of presence and titer of anti-SARS-CoV-2 IgG at baseline on treatment outcome will be assessed.

For participants receiving upamostat, targeted analysis of known host transmembrane protease polymorphisms will be described and compared to time to resolution of symptoms among key subgroups including by sex, race, and ethnicity.

C 13.5.1.5 Sub-Group Analyses

The primary analysis and each of the secondary analyses will be conducted in different patient subgroups of the mITT population for exploration of heterogeneity of treatment effect. The following patient subgroups will be analyzed:

- Age (< 30, 30-50, >50 years old)
- Sex
- Race
- Baseline symptom severity
- SARS-CoV-2 vaccination status
- Location (by continent)

C 13.6 Interim Analysis Plan

An interim analysis will be conducted when 50% (n=150) of participants have reached Day 28 of study. There are prospectively defined criteria for determining superiority of upamostat to its control arm or determining futility on upamostat to its control arm. The DSMB will evaluate safety and need to stop for safety concerns. The detailed rules for declaring superiority/futility are described in C 13.9 Sample Size Determination. Table 2 highlights the interim analysis plans for upamostat.

Table 2 Analysis Schedule and Actions Reviewed at Interim Analysis

Analysis Point	Test for Superiority	Futility Analysis	Safety Analysis
75 randomized to upamostat completing Day 28 post enrollment	Cox Proportional hazards analysis for superiority on the primary outcome; Kim-Demets alpha-spending adjustment	Futility triggered if predictive probability of superiority is less than 5%	DSMB review of safety for continued randomization
150 randomized to upamostat completing Day 28 post enrollment	Final analysis of superiority; Adjusted final nominal alpha		

The interim analyses will be conducted by an unblinded and firewalled external DSMB. The DSMB will provide any recommendations based on the interim efficacy analysis triggers and additionally will review and make recommendations on safety at each interim analysis.

The nominal alpha at the interim analysis will be calculated based on the exact sample size for the interim analysis using the Kim-Demets spending function. As an example, if there are exactly 75 patients on the upamostat arm at the interim analysis then the nominal one-sided alpha at the interim would be 0.00625 with a final analysis nominal alpha of 0.02178.

C 13.7 Final Analysis Plan

Statistical analysis of this PSA will be the responsibility of the IND Sponsor. A statistical analysis plan (SAP) will be finalized prior to the interim analysis and will provide a detailed description of the statistical analyses described in this section.

C 13.9 Sample Size Determination

The maximum sample size for the upamostat arm primary analysis is 300 participants with 1:1 allocation to the upamostat arm and its control arm. The maximum sample size of 300 participants (150 active and 150 controls) and the adaptive design provides 90% power to detect a hazard ratio of 1.50 (a 33% reduction in median time to resolution) and approximately 80% power for a hazard ratio of 1.42 (a 30% reduction in the median time to resolution).

Table 3 presents the likelihood of the trial determining superiority at the interim analysis (50%) and the final analysis for a range of assumed effect sizes for upamostat and a range of placebo median times to resolution. The expected median time to symptom resolution of 9 days for the control arm is based on review of relevant literature [[Akaishi 2022](#), [Akavian 2022](#), [Zhang 2022](#)]. The probabilities of determining futility at 50% is reported (5000 simulations pre scenario based operating characteristics in FACTS, 6.4). Simulations use a log-rank test for calculations of power as an approximation to the Cox proportional hazards model.

Table 3 Operating Characteristics for the Adaptive Design Including Superiority and Futility for a Range of Assumed Event (Symptomatic COVID-19) Rates for Upamostat Active Treatment and Upamostat Control Arm

Control Median Time to Resolution	Upamostat Hazard Ratio	Cumulative Proportion Superiority for Upamostat		Proportion Futility
		150 total	300 total	150 total
12 days	1	0.008	0.025	0.610
	1.25	0.109	0.405	0.165
	1.42	0.315	0.786	0.045
	1.50	0.436	0.883	0.021
	1.67	0.678	0.981	0.004
	2	0.939	1.000	0.000
9 days	1	0.008	0.026	0.612
	1.25	0.122	0.434	0.153
	1.42	0.340	0.812	0.035
	1.50	0.464	0.906	0.018
	1.67	0.709	0.986	0.003
	2	0.953	1.000	0.000
6 days	1	0.007	0.024	0.612
	1.25	0.131	0.458	0.138
	1.42	0.363	0.830	0.033
	1.50	0.488	0.916	0.015
	1.67	0.728	0.990	0.002
	2	0.956	1.000	0.000

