Both dose levels in this small (20-21 patients/group) study appeared to protect patients from new severe symptoms from and hospitalization for COVID-19. Several factors suggest that the 400 mg dose may be more effective than the 200 mg dose. Mean D-dimer levels were stable over the course of the study in the placebo group but decreased by 38% and 48% in the upamostat 200 mg and 400 mg groups, respectively. The only new severe on-study COVID symptom in an upamostat patient occurred in a patient in the 200 mg group. Median time to resolution of all severe symptoms was 8 days in the placebo group, 4 days in the upamostat 200 mg group, and 3 days in the upamostat 400 mg group. In summary, there was no increase in clinically significant adverse events in the 400 mg group as compared to the 200 mg group, and two parameters suggest that there may be some improvement in outcome in the high dose group as compared to the low dose group.

C 6 STUDY POPULATION AND STUDY ENROLLMENT

Population A: Adults seeking care or testing for COVID-19

C 6.1 Inclusion Criteria

Inclusion criteria are specified in the Master Protocol and:

1. **Women of childbearing potential must agree to use an effective contraceptive method upon enrollment in the study through 8 weeks after the last dose of the investigational product. This would include oral contraceptives, implanted contraceptives, intrauterine devices, and barrier methods.**
 - A woman is considered of childbearing potential unless post-menopausal (subject is at least 50 years old and has history of ≥ 2 years without menses without other known or suspected cause), or permanently surgically sterilized.
 - Participants not of reproductive potential are eligible without requiring the use of a contraceptive method. Participant-reported history is acceptable documentation of surgical sterilization and menopause.

C 6.2 Exclusion Criteria

Exclusion criteria as specified in the Master Protocol and:

1. **Patient is currently taking or is expected to start taking warfarin, apixaban (Eliquis), or rivaroxaban (Xarelto). Patients may be taking or start on study dabigatran (Pradaxa), standard or low molecular weight heparin.**
2. **Patients with prolonged QT/QTc interval and/or increased susceptibility to arrhythmia defined as the presence of any of the following:**
 - QTc interval > 450 msec
 - Pathological Q-waves (defined as Q-wave > 40 msec or depth > 0.4-0.5 mV)
 - Evidence of ventricular pre-excitation

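### The individual QTc stopping rule in C 12.1 has no absolute limit, so a baseline of 441-450 msec can pass 500 msec without meeting a mandatory stop (narrow, minor participant-safety gap)

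*Protocol*

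**What the plan says.** **Entry.** C 6.2 excludes a "QTc interval > 450 msec", so a baseline of exactly 450 msec is eligible.

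**Individual rule.** The QTc bullet in C 12.1 reads: "QTc increase >60 msec over baseline: repeat ECG within 48 hours and if >60 msec increase over baseline persists, IP will be discontinued". It is relative to baseline only. The list it belongs to is open: "The individual pause and stopping criteria will include (but not be limited to) the following". The paragraph before the list also lets the investigator or medical monitor interrupt or stop dosing for a suspected drug-related event suggesting QTc prolongation.

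**Study-level rule.** Table 1 in C 12.2 has two QTc limbs, ">500 msec OR QTc" more than "60 msec above baseline on repeat ECG within 48 hours". The actions are reporting within 24 hours, considering a pause of the product-specific arm, and trend monitoring by the PSRT. The table is headed as criteria for a study pause and covers events related to the investigational product.

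**ECG schedule.** The Schedule of Activities (C 1.2) marks ECGs at screening or baseline, Day 3, Day 14 and unscheduled visits. Dosing is daily for 14 days from Day 0.

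**Reporting.** SAP 5.2.7 plans summaries of QTc and of change from baseline by visit, plus a listing. It plans no count of values above 500 msec.

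**The concern.** The protocol regards 500 msec as serious enough to raise a pause of the whole arm, yet the participant who reaches it need not meet any numeric stopping rule in C 12.1. The result is uneven. A move from 400 to 461 msec requires a repeat ECG and, if confirmed, a stop. A move from 450 to 510 msec meets no listed rule in C 12.1, although the QTc reached is much longer.

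For the laboratory parameters the two levels use the same grade threshold. In C 12.1, coagulation is "INR, PTT: increase over baseline > 2 Grades", and Table 1 has "> 2 Grade increase in verified PT, PTT or INR >2 patients". In C 12.1, liver is "Transaminases, bilirubin: increase over baseline >1 Grade above baseline: pause therapy", and Table 1 also uses more than one grade. Only QTc has a study-level limb with no individual counterpart, and the appendix gives no reason for that.

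What is at stake is the safety of an occasional participant. The efficacy comparison is not affected.

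**Working it through.** **Where the gap lies.** The inputs are the entry ceiling of 450 msec (C 6.2), the rise of more than 60 msec (C 12.1) and the value above 500 msec (Table 1). For baseline *b* and on-treatment QTc *q*, in whole msec, a case is in the gap when *q* > 500 and *q* − *b* ≤ 60. This requires *b* + 60 > 500, so *b* ≥ 441. The smallest rise that passes 500 is 501 − *b*.

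| Baseline (msec) | Rise needed to reach 501 | QTc values in the gap |
|---|---|---|
| 440 | 61 (already meets the +60 rule) | none |
| 441 | 60 | 501 |
| 445 | 56 | 501-505 |
| 450 | 51 | 501-510 |

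Over baselines 441 to 450 this gives 1 + 2 + … + 10 = 55 baseline/QTc pairs. At 440 msec or below there are none. With an absolute limb at 500 msec added to the C 12.1 rule, no pairs remain.

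**When the next scheduled ECG falls.** Day 3 (±1) to Day 14 (±2) is nominally 11 days, with a minimum of 12 − 4 = 8 and a maximum of 16 − 2 = 14. Doses run from Day 0 to Day 13. After a Day 3 ECG there are nominally 10 more doses (Days 4-13), or 11 if the ECG precedes the Day 3 dose. If the Day 14 visit is held on Day 12, as its window allows, the ECG can fall before the course ends. The gap therefore matters mainly at Day 3 and at unscheduled ECGs.

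**How often it would happen.** The documents give no QTc distribution, so the following is assumed: baseline normal with mean 410-430 and SD 15-20 msec, cut at 450; change normal with mean *m* and SD 15-20 msec, independent of baseline. The probability per ECG is P(*q* > 500 and *q* − *b* ≤ 60).

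- No mean shift (*m* = 0): 1.57 × 10⁻⁶ to 3.11 × 10⁻⁴. Times 300 participants, this is 0.0005 to 0.093.
- Mean shift of +20 msec: 9.40 × 10⁻⁵ to 3.12 × 10⁻³. Times 150 treated participants, this is 0.014 to 0.468.

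Two adjustments, each taken alone, lower these figures:

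- *Sample size.* SAP Appendix A says enrollment ended before the interim trigger, which C 13.6 sets at 150 participants (75 on upamostat) reaching Day 28. Halving the numbers brings the upper ends to 0.093/2 = 0.047 and 0.468/2 = 0.234.
- *Regression to the mean.* Participants measured at 441-450 msec sit at the top of a truncated range. If baseline and follow-up variances are assumed equal, the correlation of change with baseline is −SD(change)/(2 × SD(baseline)). The upper ends then fall to about 0.005 of 300 and 0.10 of 150.

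**The case against.** The strongest reply is that the participant is not left without protection. C 12.1 names QTc prolongation as a ground for interrupting or stopping dosing, and it allows a stop for any clinically significant adverse event. Its list is open, unscheduled ECGs are provided for, and Table 1 requires 24-hour reporting of a product-related QTc above 500 msec. All of this stands. A reader might infer that such a participant simply continues dosing by default; the documents do not support that. What is missing is a mandatory rule. The same discretion covers liver and coagulation effects, and there the protocol wrote mandatory numeric rules as well.

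A second reply concerns Table 1's repeat-ECG phrase. If it governs both limbs, it implies a repeat ECG for a value above 500 msec. So it goes too far to say that no repeat is required anywhere; only C 12.1 is silent. On either reading, Table 1 sets no individual stop.

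Third, study-level and individual triggers need not be identical, and the laboratory match is in the grade threshold only. Table 1 also asks for verified values in more than two patients, adds PT, and limits the coagulation row to those not on anticoagulants. That weakens the comparison but does not explain why a 500 msec limit is absent for the individual.

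Fourth, the Master Protocol was not available and may contain further individual rules. This cannot be settled from the two documents.

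Fifth, a +20 msec shift is only an assumption. C 3.4.1.1 and C 5.4 report no QTc effect of upamostat. This is correct, and it makes the lower set of figures the more natural one.

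**Conclusion.** The point holds as a narrow, minor participant-safety gap. For baselines of 441-450 msec, a QTc of 501-510 msec can occur without meeting any mandatory individual stop listed in Appendix C, and C 12.1 itself does not require a repeat ECG there. The arithmetic is exact in whole msec and needs no assumption beyond the three thresholds.

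The frequency does rest on assumptions. Under all those shown, the expected number is well under one case, and lower still given the early end of enrollment. Neither a QTc effect of the drug, nor a between-arm bias, nor any effect on the primary analysis should be inferred from this point. It is also conditional on the Master Protocol holding no individual rule that closes the gap.

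**What to change.** In any reuse of the appendix, give the C 12.1 bullet an absolute limb. A QTc above 500 msec, or a rise of more than 60 msec from baseline, should lead to a repeat ECG within 48 hours, and the product should be discontinued if either finding persists. This is a one-line change, it uses a threshold the protocol already has, and it removes the dependence on how Table 1 is read. The cost is a few extra repeat ECGs or product stops, some of them in placebo participants.

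Enrollment has ended, so that change protects nobody in this trial. Here, add to the SAP 5.2.7 output a count by arm of participants with any post-baseline QTc above 500 msec. For those whose rise was 60 msec or less, state whether the ECG was repeated and whether dosing was stopped. The ECG values are already to be listed, so the extra work is a short tabulation and a check of the individual records.
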